#### **2) Harms:**

No Harms are expected. But if any adverse effect occurs then the senior supervisor has the right to call for stopping the trial if more than 30% of cases showed any harms or side effects.

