## 2) Trial design:

Randomized clinical Trial, parallel arms.

Trial framework: Equivalence frame

Allocation ratio: 1:1.

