## 2) Participant timeline: (Table 2)

Activity	Staff member	T0 Baseline	T1 After 5 min	T2 After 15 days
Recruitment	Y.S.	X		
Diagnosis	Y.S.	X		
Consent	Y.S.	X		
Baseline data collection	Y.S.	X		
Randomization	Y.S.	X		
Saliva & Plaque sampling	M.A.	X	X	X
Outcome assessment	H.M. E.M.	X	X	X

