## 3) Sample size calculation:

A power analysis was designed to have adequate power to apply statistical test of the research hypothesis that dissolving xylitol chewing tablets will have the better antibacterial effect than xylitol chewing gum against mutans streptococci after 1 month. According to the results of *Swapnil et al. in 2018* in which the probability of bacterial count reduction to  $10^2$  for xylitol chewing gum (comparator) was (0.15), probability of bacterial count reduction to  $10^3$  was (0.6) and probability of bacterial count reduction to  $10^4$  was (0.25) with effect size  $w=0.578$  ( $n=29$ ). If the estimated probability of dissolving xylitol chewing tablets for bacterial count reduction to  $10^2$  is (0.35), probability of bacterial count reduction to  $10^3$  is (0.5) and probability of bacterial count

reduction to  $10^4$  was (0.15) with effect size  $w=0.43$  ( $n=53$ ). By adopting an alpha ( $\alpha$ ) level of 0.05 (5%), power=80%. The predicted sample size ( $n$ ) was a total of (82). Sample size was increased by (20%) to account for possible dropouts during follow-up intervals to be total of (98) cases i.e. (49) for each group. Sample size calculation was performed using G\*Power 3.1.9.2.

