### **D)Monitoring:**

#### **1) Data monitoring:**

The main supervisor (A.E.) will monitor this study. His role is to monitor any risk of bias from participants, operator or assessors, monitor blinding of the assessors and monitor patient safety, outstanding benefits or harms.

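### The 30% harm clause has no planned count of harms behind it and no stated denominator

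*Protocol*

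**What the plan says.** Section III.D 2) Harms opens with "No Harms are expected". It then gives a discretionary power on a condition: "the senior supervisor has the right to call for stopping the trial if more than 30% of cases showed any harms or side effects". It names no arm, severity grade, denominator or time of assessment.

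Section III.D 1) Data monitoring asks the main supervisor to "monitor patient safety, outstanding benefits or harms". It does not say from which records or when.

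Table 2 (Participant timeline) schedules recruitment, diagnosis, consent, baseline data, randomization, "Saliva & Plaque sampling" and outcome assessment at baseline (T0), 5 minutes (T1) and 15 days (T2). It has no row for harms. The outcomes in section 2.3 and Table 1 are two bacterial counts and salivary pH.

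The sample size section uses the word cases for the whole sample: "total of (98) cases i.e. (49) for each group". The trial design section gives "Allocation ratio: 1:1".

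**The concern.** A rule that depends on a percentage needs a count to divide and a number to divide it by. The protocol plans neither. The supervisor would have to rely on whatever harms happen to be mentioned, and two people applying the same sentence could reach opposite answers.

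The arms also receive different products used in different ways (section III.A 3, Interventions): a tablet that is chewed, swished and swallowed, and a gum that is chewed for 5 minutes. Harms could therefore differ by arm. If the share is taken over both arms together, a problem confined to one product is diluted by the other.

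At stake are the usefulness of the clause as a safeguard in bedridden patients over 65 recruited from intensive care units, and the completeness of any later comparison of harms between the products.

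**Working it through.** **1. Is there a planned numerator?** Each section that could supply one:

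- Table 2: no harm activity at T0, T1 or T2.
- Section 2.3 and Table 1 (outcomes): salivary and plaque bacterial counts and salivary pH only.
- Section III.C 1.1 (baseline data): medical and dental history and examination charts, before treatment.
- Section III.C 1.2 (outcome data): scoring of the listed outcomes at the three times.
- Section III.C 1.3 (retention): calls and messages that serve as reminders.
- Section III.D 1 (data monitoring): a responsibility, with no source, method or time.

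None of them produces a count of patients with a harm.

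**2. The whole-sample denominator.** The sample size section adds 29 and 53 to get 82, then inflates by 20%: 82 × 1.20 = 98.4, stated as 98, or 98 / 2 = 49 per arm. The figure reproduces.

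**3. What the clause means under each reading of the denominator.**

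- All 98 enrolled: 0.30 × 98 = 29.4, so exceeding 30% takes 30 patients (30/98 = 30.6%); 29 do not reach it (29/98 = 29.6%).
- Each arm of 49: 0.30 × 49 = 14.7, so 15 patients in one arm (15/49 = 30.6%).
- Patients treated so far: 1 of the first 3 (33.3%) already exceeds it.

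**4. Largest share of one arm that stays under the whole-sample threshold.** With x affected in the other arm, this is (29 − x) / 49:

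| Affected in other arm | Largest share in this arm |
|---|---|
| 0 of 49 | 29/49 = 59.2% |
| 2 of 49 | 27/49 = 55.1% |
| 5 of 49 | 24/49 = 49.0% |
| 10 of 49 | 19/49 = 38.8% |

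With the 82 patients before dropout inflation: 0.30 × 82 = 24.6, and 24/41 = 58.5%. Simple randomization need not give exactly 49 per arm: 29 affected is 72.5% of an arm of 40 and 53.7% of an arm of 54.

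**5. Chance of reaching 30 at full enrolment.** This is P(X₁ + X₂ ≥ 30), with X₁ ~ Bin(49, p₁) and X₂ ~ Bin(49, p₂). The rates are illustrative assumptions, because the protocol gives none.

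| p₁ | p₂ | Chance of reaching 30 |
|---|---|---|
| 40% | 0% | 0.2% |
| 50% | 0% | 7.6% |
| 59% | 0% | 43.5% |
| 40% | 10% | 10.8% |
| 50% | 10% | 48.7% |

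**The case against.** Several stronger readings are tempting, and the protocol does not support them.

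- **That the trial stops at 30%, or that nobody can act below it.** The clause gives a right to call for stopping. It neither compels a stop nor forbids earlier action, and the data monitoring section gives oversight of safety without any threshold.
- **That the rule is written as pooled.** It is not. Pooling is inferred from the word cases as used in the sample size section. The inference is reasonable, but a per-arm meaning is not excluded.
- **That nearly 60% of an arm would typically go unnoticed.** The 59% needs no harms at all in the other arm, exactly 49 per arm and full enrolment. The products share xylitol, sucralose and acesulfame potassium, so some complaints in both arms are plausible and the figure falls accordingly.
- **That a harm specific to one product cannot be detected, or that harms could not be reported by arm.** Thirty affected in a single arm would exceed the threshold, and any harm that is noted can be tabulated by arm because allocation is recorded.
- **That safety monitoring has no data at all.** Spontaneous reports may reach the supervisor. Table 2 is not a full schedule, since it also omits product administration and the reminder calls. Some pages, including consent pages, were not available for review.

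All of this limits the claim. It does not supply a planned numerator or a stated denominator, and these are not details commonly left to a statistical analysis plan, because the protocol itself sets both the clause and the visit schedule.

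**Conclusion.** The point holds in a limited form. In the protocol as shown, the 30% share cannot be calculated from planned data collection, and the sentence admits at least three denominators that need 30 patients in total, 15 in one arm, or as few as 1 of the first 3. Because the clause is discretionary, this is a weak and ambiguous safeguard, not a mis-set automatic stop.

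The size of the dilution rests on reading cases as all 98 and on 49 per arm. On that basis the share of one arm that stays under the threshold is 59% at worst, and 49% or 39% with 5 or 10 affected in the other arm. If the sponsor means the share per arm, the dilution disappears but the missing numerator remains. The change should be made before recruitment, since harms not asked about at the visits cannot be recovered reliably afterwards.

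**What to change.** Add a row to Table 2 for recording harms at the existing T1 and T2 visits, noting arm, date and seriousness, with T2 covering the interval since the first dose. Harms can then be counted and reported by arm.

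Reconcile Table 2 and the sections on outcome data collection, data monitoring and harms, so that the sponsor states:

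- the denominator of the share;
- whether the share is pooled or per arm;
- when it is examined;
- whether the main supervisor in one section and the senior supervisor in the other are the same person.

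The threshold, the stopping rule and the handling of serious events are for the sponsor to set, and none is proposed here.

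The cost is a short question at two planned visits, one table row and some wording. There is one practical burden: the operator and both assessors are to be blinded, and the operator also enters the data. The by-arm tabulation must therefore be kept from all three and done by someone else with access to the allocation.

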### **3) Auditing:**

In this trial auditing will be done by the main and co-supervisors (A.E., A.H. & O.S.) to assure quality of the research methods, sampling techniques and interventions.

## **IV) ETHICS AND DISSEMINATION:**

### **1) Research ethics approval:**

Application forms for accomplishing clinical trial, checklist and informed consent of Research Ethics Committee (REC) Faculty of Oral and Dental Medicine, Cairo University will be retrieved and filled, then will be delivered for REC committee for approval, this is done to prevent any ethical problems during the study or any harms for any of the participants.

### **2) Protocol amendments:**

If a new protocol will be used a protocol amendment will be submitted, containing a copy of the new protocol and a brief explanation about the differences between it and the previous protocols. If there is a change in the existing protocol that affect safety of subjects, investigation scope, or scientific quality of the trial an amendment containing a brief explanation about the change must be submitted. If a new author will be added to accomplish the study an amendment including the investigator's data and qualifications to conduct the investigation will be submitted to prevent ghost authorship.

### **3) Consent or assent:**

Y.S. is responsible of admitting and signing the informed consents during enrollment day.

#### **4) Confidentiality:**

The name and the personal data of the participants will not appear on the protocol form and should be maintained secured for 10 years after the trial. This is done for protection of participants' privacy and civil rights.

#### **4) Declaration of interests:**

There is no conflict of interest, no funding or material supplying from any parties.

#### **5) Access to data:**

Access to final data will be allowed to M.A. and the main and co-supervisors (A.E., A.H. & O.S.) who are not involved in assessment of the outcome.

#### **6) Ancillary and post-trial care:**

Patients will be followed up after the end of the study period to ensure oral hygiene measures.

#### **7) Dissemination policy:**

- Full protocol will be published online in <https://clinicaltrials.gov/> to avoid repetition, and keep the integrity of the research work.
- Thesis will be discussed in front of a judgment committee.
- The study will be published to report the results of the clinical trial.

